**Table 6.1. Patient Populations**

Population	Description
Entered	All patients who give informed consent.
Enrolled	All patients who receive at least 1 dose of open-label insulin lispro in the 8-week lead-in period.
Randomized	All patients who are randomly assigned to study treatment at Visit 8. Treatment group will be defined on the basis of the treatment the patients are assigned.
Safety	All randomized patients who receive at least 1 dose of the randomly assigned investigational product (IP). Treatment group will be defined on the basis of the treatment the patients are assigned.
Completer	Patients included in the randomized population who have completed Week 26 of study treatment without permanent discontinuation of IP. Treatment group will be defined on the basis of the treatment the patients are assigned.
Per Protocol	Patients included in the randomized population who have completed Week 26 of study treatment without permanent discontinuation of IP and without significant protocol deviations through Week 26 that would significantly impact the primary objective. Treatment group will be defined on the basis of the treatment the patients actually receive.

Unless otherwise stated, the efficacy analyses will be conducted on the Randomized Population, and the safety analyses will be conducted on the Safety Population.

The primary analysis is for the treatment period through Week 26.

Unless otherwise noted, all tests of treatment effects will be conducted at a 2-sided alpha level of 0.05, and CIs will be calculated at 95%, 2-sided. All tests of interactions between treatment groups and other factors will be conducted at a 2-sided alpha level of 0.10.

The definitions of baseline and post-baseline for the efficacy and safety analyses depend on which analysis period is being used. The following analysis periods will be used:

- Lead-in Period – Visits 2 to 8
- 26-Week Treatment Period – from randomization to Week 26 prior to discontinuation of investigational product (IP)
- 
- 26-Week Treatment Period and Safety Follow-Up Visit – from randomization to Visit 801 (including all data regardless of IP use)

The data on IP is defined based on the following rules:

- For data only measured at an office visit
  - Mixed-meal tolerance test (MMTT) postbaseline data will be classified as on IP if the MMTT performance date is prior to or on the last IP dose date

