## 6.11. Efficacy Analyses

### 6.11.1. Primary Outcome and Methodology

The primary objective of this study (H1) is to test the hypothesis that LY900014 is noninferior to insulin lispro on glycemic control (NIM=0.4% for HbA1c) in patients with T2D, when administered as prandial insulin (0 to 2 minutes prior to the meal), in combination with basal insulin for 26 weeks.

The primary efficacy comparison will be based on the contrast between LY900014 and insulin lispro at Week 26 (Visit 18) from the MMRM analysis of change from baseline in HbA1c including data collected from all randomized patients prior to permanent discontinuation of IP through Week 26. The model for the analysis of the primary efficacy endpoint of change from

baseline in HbA1c will include the fixed class effects of treatment, strata (country, type of basal insulin during the lead-in period, and number of prandial doses at study entry), visit, and treatment-by-visit interaction, as well as the continuous, fixed covariates of baseline value. An unstructured covariance structure will be used to model the within-patient errors. Significance tests will be based on LS means and Type III tests. If this analysis fails to converge, the following covariance structures will be tested in order:

- Toeplitz with heterogeneity
- autoregressive with heterogeneity
- compound symmetry with heterogeneous variances
- Toeplitz
- autoregressive
- compound symmetry without heterogeneous variances

The first covariance structure that converges will be used. The Kenward-Roger approximation will be used to estimate denominator degrees of freedom.

For both primary analysis approaches, LY900014 will be declared noninferior to insulin lispro if the upper limit of the 2-sided 95% CI for the LS mean difference in the change from baseline in HbA1c for LY900014 minus insulin lispro is below +0.4%.

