A listing of anti-insulin lispro antibody at each visit will be provided. The listing will include anti-insulin lispro antibody status (detected/not detected), anti-insulin lispro antibody percent binding, TEADA status (positive/negative), insulin cross-reactivity status, and insulin cross-reactivity percent binding for the safety population.

Subgroup analysis for the following selected efficacy and safety variables will be performed by the TEADA status during the analysis period of Visit 2 to Visit 801:

- Use data prior to discontinuation of IP:
  - HbA1c and change from baseline in HbA1c
  - 1-hour and 2-hour PPG excursions
  - basal, prandial, and total insulin dose
  - event rate of overall hypoglycemic events
- Use all data regardless of IP use:
  - treatment-emergent injection site reaction and hypersensitivity reaction

The analyses for HbA1c and change from baseline in HbA1c will be performed using an MMRM model for the primary analysis and the HbA1c data prior to permanent discontinuation of IP. Besides treatment, the model will include additional fixed terms of subgroup, subgroup by treatment interaction, subgroup by visit interaction, and 3-way interaction of treatment, subgroup and visit.

The PPG excursions will be analyzed by the ANCOVA model same as the model specified in Section 6.11.2 with data collected before permanent discontinuation of IP. The model will include additional terms of subgroup, subgroup by treatment interaction, subgroup by visit interaction, and 3-way interaction of treatment, subgroup and visit.

The subgroup analysis for insulin dose will use the MMRM model specified in Section 6.11.5 using data collected before permanent discontinuation of IP. The model will include additional

fixed terms of subgroup, subgroup by treatment interaction, subgroup by visit interaction, and 3-way interaction of treatment, subgroup and visit.

The treatment-emergent injection site reaction and hypersensitivity reaction will be analyzed by a logistic regression model including terms of treatment, subgroup, treatment by subgroup interaction. All data regardless of IP use will be used for this analysis.

The negative binomial regression model specified in [Table 6.5](#) with additional terms of subgroup, treatment by subgroup interaction will be used for the subgroup analysis of overall hypoglycemia event rate while on IP.

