The interaction effects (3-way for MMRM and 2-way for ANCOVA/logistic regression model/negative binomial regression model) will be evaluated using a significance level of 0.10, unadjusted. If the interaction effect is significant ( $p < 0.10$ ), separate analysis without the terms related with the subgroup will be performed for each subpopulation.

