## **6.13. Subgroup Analyses**

### **6.13.1. Subgroup Analyses for HbA1c**

The following subgroups will be analyzed for HbA1c if there are sufficient numbers of patients per group (for example, at least 10% in each group):

- age (<65 versus  $\geq 65$  years and <75 vs.  $\geq 75$  years and <65,  $\geq 65$  to <75,  $\geq 75$  to <85,  $\geq 85$  years)
- baseline hemoglobin A1c stratum ( $\leq 8.5\%$  vs.  $> 8.5\%$ )
- sex (male vs. female)
- body mass index (<25 vs.  $\geq 25$ , and <30 vs.  $\geq 30$  kg/m^2 and <35 vs.  $\geq 35$  kg/m^2)
- duration of diabetes (using the median as the cut-off)
- race
- country
- region

- baseline 1-hour PPG excursion ( $\leq$  baseline median,  $>$  baseline median)
- baseline 1-hour PPG (PPG  $\leq$ 180 mg/dl,  $>$ 180 mg/dl)
- baseline 2-hour PPG excursion ( $\leq$  baseline median,  $>$  baseline median)
- baseline 2-hour PPG (PPG  $\leq$ 180 mg/dl,  $>$ 180 mg/dl)
- type of basal insulin during the lead-in period (glargine vs. degludec)
- prandial insulin dosing plan (carbohydrate counting or pattern adjustment)
- number of prandial doses at study entry ( $<$ 3 vs.  $\geq$ 3)
- sodium-glucose co-transporter 2 inhibitor treatment

Analyses for HbA1c and change from baseline in HbA1c will be performed using an MMRM model that includes the same fixed effects given for the primary analysis model plus factors of subgroup, 2-way interaction of subgroup and treatment, 2-way interaction of subgroup and visit, and 3-way interaction of treatment, visit and subgroup. The interaction of subgroup and treatment at the primary endpoint will be evaluated to assess the treatment by subgroup interaction. When analyzing HbA1c stratum as a subgroup the baseline HbA1c will be not be included as a covariate to avoid confounding. The subgroup interaction effect will be evaluated using a significance level of 0.10, unadjusted.

Additional subgroup analyses may also be performed.

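### The antibody-status (TEADA) subgroup MMRMs are judged by the 3-way interaction with visit, which does not test whether the treatment effect at Week 26 differs by antibody status, and SAP 6.13.1 uses a different rule

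*SAP*

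**What the plan says.** SAP 6.12.7.1 plans subgroup analyses by TEADA status for HbA1c, insulin doses, PPG excursions, overall hypoglycemia rate, and injection-site and hypersensitivity reactions. HbA1c and the doses are analyzed by MMRM. For HbA1c, "the model will include additional fixed terms of subgroup, subgroup by treatment interaction, subgroup by visit interaction, and 3-way interaction of treatment, subgroup and visit". For doses, "The subgroup analysis for insulin dose will use the MMRM model specified in Section 6.11.5", with the same added terms.

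The decision rule at the end of the section is "The interaction effects (3-way for MMRM and 2-way for ANCOVA/logistic regression model/negative binomial regression model) will be evaluated using a significance level of 0.10". If that test is significant, "separate analysis without the terms related with the subgroup will be performed for each subpopulation". The 0.10 level is the general one in SAP 6.1: "All tests of interactions between treatment groups and other factors will be conducted at a 2-sided alpha level of 0.10". SAP 6.11.1 says of the primary MMRM, on which the HbA1c subgroup model is built: "Significance tests will be based on LS means and Type III tests".

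SAP 6.13.1 fits the same kind of model for the other HbA1c subgroups (age, sex, BMI, country, type of basal insulin and so on), but there "The interaction of subgroup and treatment at the primary endpoint will be evaluated to assess the treatment by subgroup interaction".

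For the PPG excursions, SAP 6.12.7.1 names an ANCOVA and then adds: "The model will include additional terms of subgroup, subgroup by treatment interaction, subgroup by visit interaction, and 3-way interaction of treatment, subgroup and visit".

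**The concern.** Once treatment-by-subgroup and subgroup-by-visit terms are in an MMRM, the 3-way term measures only departures of the treatment-by-subgroup difference from its average over visits. A difference of the same size at every visit sits wholly in the 2-way term, which the 6.12.7.1 rule does not test for MMRMs. An early difference that has disappeared by Week 26 goes partly into the 3-way term and can make it significant.

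The trial's HbA1c endpoint is at Week 26, and 6.13.1 places the subgroup question there. So the SAP has two rules for the same kind of question and gives no reason for the difference. At stake are the statement of whether antibody status modifies the treatment effect on HbA1c and dose, and the trigger for the separate refits by status.

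**Working it through.** **Inputs from the documents.** 320 LY900014 and 160 insulin lispro completers, SD 1.1% and margin 0.4% (SAP 5.2). Post-baseline HbA1c at Visits 11, 13, 15 and 18 (SAP Table 6.2), which are Weeks 4, 8, 12 and 26. Interaction level 0.10.

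**Assumptions.** The documents give no TEADA-positive share, within-patient correlation or interaction size. I take a share q = 0.3, an exchangeable correlation ρ = 0.7, SD 0.9 to 1.1 and complete data. Interaction sizes are in HbA1c percentage points.

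**The plan's own figure first.** SE = 1.1 × √(1/320 + 1/160) = 0.1065. Power = Φ(0.4/0.1065 − 1.96) = 0.964, against the stated 96%. 480/0.85 = 564.7, against about 564. Both reproduce. The point does not depend on them.

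**Set-up.** Let d be the vector of treatment-by-TEADA differences at the four visits. Its estimate has covariance kΣ, where k sums 1/n over the four cells:

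k = 1/96 + 1/224 + 1/48 + 1/112 = 0.0446

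- *3-way test:* are the four elements of d equal? This has 3 df, with chi-square critical value 6.25 at 0.10. With exchangeable correlation the noncentrality is Σ(d_j − mean d)² / [k × SD² × (1 − ρ)].
- *Week 26 contrast:* z = d_26/(SD√k), 1 df, two-sided 0.10. SE = 0.190 (SD 0.9) to 0.232 (SD 1.1).

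**Worked case, SD 1.1, d = (0.4, 0.3, 0.2, 0).** Σ(d_j − 0.225)² = 0.0875. Noncentrality = 0.0875/(0.0446 × 1.21 × 0.3) = 5.40, which gives rejection probability 0.60. The Week 26 element is 0, so the contrast rejects at 0.10.

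| Difference at Weeks 4, 8, 12, 26 | 3-way test | Week 26 contrast |
|---|---|---|
| 0.4, 0.4, 0.4, 0.4 | 10% | 53-68% |
| 0.6, 0.6, 0.6, 0.6 | 10% | 83-93% |
| 0.4, 0.3, 0.2, 0 | 60-77% | 10% |
| 0.1, 0.2, 0.3, 0.4 | 40-54% | 53-68% |
| 0, 0.1, 0.2, 0.4 | 60-77% | 53-68% |

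Ranges run from SD 1.1 to SD 0.9. The third and fifth rows have the same sum of squares, so the 3-way test gives the same answer for an interaction that has vanished and one that is at its largest at Week 26.

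**Sensitivity.** For a constant difference the noncentrality is exactly zero whatever q, ρ or SD, so 10% does not depend on the assumptions. With SD 1.1 and q = 0.2, 0.3 and 0.5, the Week 26 contrast finds a constant 0.4% with power 0.44, 0.53 and 0.59. Over q = 0.2 to 0.5 and ρ = 0.5 to 0.8 (SD 1.1), the 3-way test flags the vanished pattern in the third row 34-83% of the time, and has power 24-61% for the steady build-up in the fourth row.

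**Simulation check** (4000 runs, q = 0.3, ρ = 0.7, SD 1.1, unstructured covariance). Constant 0.4: 0.100 against 0.533. Constant 0.6: 0.097 against 0.828. (0.4, 0.4, 0.2, 0): 0.691 against 0.102.

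**Doses.** Table 6.2 as extracted shows Visits 15 and 18. With two visits the 3-way term has 1 df and the pattern is the same: a constant difference is flagged at 10%. On the HbA1c scale, with SD 1.1, a difference of 0.4 falling to 0 is flagged 72% of the time.

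**The case against.** Four points on the other side deserve weight.

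1. *By-status results are not withheld.* A reader might infer that a non-significant 3-way test suppresses the estimates by TEADA status. The text does not support that. The subgroup analysis is planned unconditionally, the joint model holds every term needed for the Week 26 treatment difference in each status group, and SAP 6.1 displays LS means and treatment differences with CIs from the analysis models. The p<0.10 rule gates only the extra refits. This stands.

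2. *The 3-way test is not blind to every Week 26 difference.* It keeps power for one that builds up, and for 0, 0.1, 0.2, 0.4 it has somewhat more than the contrast. Such a pattern is plausible, since prandial doses are titrated over the first 12 weeks. This also stands. It limits the size of the problem, but the test still answers a different question.

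3. *The PPG wording changes no result.* It is tempting to count the visit terms in the PPG ANCOVA as a second analytical error. But the decision rule already assigns the 2-way test to ANCOVA, and with one post-baseline MMTT the visit terms cannot be estimated and would drop out. That is editorial.

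4. *The analysis is supportive.* TEADA incidence is a tertiary objective and efficacy by TEADA status is not a listed endpoint. Status is also classified after randomization, on all data to Visit 801, so neither test gives a clean causal answer about antibodies. This lowers the stakes. It does not explain why 6.12.7.1 and 6.13.1 should use different tests.

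**Conclusion.** The point holds for the TEADA MMRMs (HbA1c and insulin doses). As written, effect modification is judged, and the refits are triggered, by a test of change over visits. It has no power beyond its 10% level for a constant difference; that follows from the algebra alone. The other figures are illustrative and rest on the assumed 30% TEADA-positive share, SD 0.9 to 1.1, correlation 0.7 and interaction sizes: 53-68% for the Week 26 contrast with a constant 0.4%, and 60-77% against 10% for a difference gone by Week 26.

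The consequence is confined to the stated interaction conclusion and the decision to run the separate refits. The logistic, negative binomial and ANCOVA subgroup models use the 2-way test and are not affected. Nothing here touches the primary or multiplicity-adjusted tests. It should be corrected because the two sections conflict and the correction is almost free.

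**What to change.** In SAP 6.12.7.1, for the HbA1c and insulin dose MMRMs, replace the 3-way test with the treatment-by-subgroup contrast at Week 26 from the same model, as in 6.13.1. Base the p<0.10 rule for the separate refits on that contrast. Keep the 3-way test as a descriptive check on whether the difference varies over time.

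As an editorial change, remove the visit terms from the PPG subgroup model when the ANCOVA is used, leaving treatment, subgroup and their interaction. Do not extend that deletion to the constrained longitudinal model that 6.11.2 substitutes when more than 15% of baseline MMTT data are missing.

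Cost: two edited sentences and one contrast statement. No new data or model is needed.

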### **6.12.8. Patient Narratives**

Patient narratives will be provided for all patients in the study who experience any of the following “notable” events prior to data cutoff for the submission:

- deaths
- serious adverse events
- discontinuations from study (or study drug) due to AEs
- pregnancy

A list of patients who meet the criteria for narratives will be provided.

## **6.13. Subgroup Analyses**

### **6.13.1. Subgroup Analyses for HbA1c**

The following subgroups will be analyzed for HbA1c if there are sufficient numbers of patients per group (for example, at least 10% in each group):

- age (<65 versus  $\geq 65$  years and <75 vs.  $\geq 75$  years and <65,  $\geq 65$  to <75,  $\geq 75$  to <85,  $\geq 85$  years)
- baseline hemoglobin A1c stratum ( $\leq 8.5\%$  vs.  $> 8.5\%$ )
- sex (male vs. female)
- body mass index (<25 vs.  $\geq 25$ , and <30 vs.  $\geq 30$  kg/m^2 and <35 vs.  $\geq 35$  kg/m^2)
- duration of diabetes (using the median as the cut-off)
- race
- country
- region

- baseline 1-hour PPG excursion ( $\leq$  baseline median,  $>$  baseline median)
- baseline 1-hour PPG (PPG  $\leq$ 180 mg/dl,  $>$ 180 mg/dl)
- baseline 2-hour PPG excursion ( $\leq$  baseline median,  $>$  baseline median)
- baseline 2-hour PPG (PPG  $\leq$ 180 mg/dl,  $>$ 180 mg/dl)
- type of basal insulin during the lead-in period (glargine vs. degludec)
- prandial insulin dosing plan (carbohydrate counting or pattern adjustment)
- number of prandial doses at study entry ( $<$ 3 vs.  $\geq$ 3)
- sodium-glucose co-transporter 2 inhibitor treatment

Analyses for HbA1c and change from baseline in HbA1c will be performed using an MMRM model that includes the same fixed effects given for the primary analysis model plus factors of subgroup, 2-way interaction of subgroup and treatment, 2-way interaction of subgroup and visit, and 3-way interaction of treatment, visit and subgroup. The interaction of subgroup and treatment at the primary endpoint will be evaluated to assess the treatment by subgroup interaction. When analyzing HbA1c stratum as a subgroup the baseline HbA1c will be not be included as a covariate to avoid confounding. The subgroup interaction effect will be evaluated using a significance level of 0.10, unadjusted.

Additional subgroup analyses may also be performed.

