## 6.2. Adjustments for Covariates

Stratification factors of this study include country (China vs. Other), HbA1c stratum at baseline ( $\leq 8.5\%$  vs.  $>8.5\%$ ), type of basal insulin during the lead-in period (glargine U-100 vs. degludec U-100), and number of prandial doses at study entry ( $<3$  vs.  $\geq 3$ ).

For the primary analysis of HbA1c, the stratification factor of HbA1c stratum (baseline) will not be included. Instead, the continuous value of baseline (Visit 8) HbA1c will be included in the analysis models.

Other efficacy analyses and safety analysis will include the stratification factors as noted in Sections [6.11](#) and [6.12](#).

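### Dropping continuous baseline HbA1c from the HbA1c-stratum subgroup model costs precision, and confounding is not a valid reason; centring baseline within stratum would keep it

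*SAP*

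**What the plan says.** SAP 6.13.1 sets one general model for the HbA1c subgroups. It "includes the same fixed effects given for the primary analysis model plus factors of subgroup", followed by the subgroup-by-treatment, subgroup-by-visit and three-way interactions. Those primary-model effects come from SAP 6.11.1: treatment, three stratification factors, visit and treatment-by-visit, "as well as the continuous, fixed covariates of baseline value". Two responses are planned: "Analyses for HbA1c and change from baseline in HbA1c will be performed using an MMRM model".

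One exception follows. When the HbA1c stratum is itself the subgroup, "baseline HbA1c will be not be included as a covariate to avoid confounding". The stratum and its interactions stay in that model.

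The section names its target, "The interaction of subgroup and treatment at the primary endpoint will be evaluated to assess the treatment by subgroup interaction", and its test level, "The subgroup interaction effect will be evaluated using a significance level of 0.10, unadjusted".

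SAP 6.2 makes the opposite choice for the primary model: "For the primary analysis of HbA1c, the stratification factor of HbA1c stratum (baseline) will not be included", and continuous baseline is used in its place.

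**The concern.** A covariate confounds a treatment comparison only if it is related to both treatment and outcome. Baseline HbA1c and the stratum derived from it both precede randomization, so apart from chance neither is related to treatment. The reason the SAP gives therefore does not apply to the quantity it sets out to test.

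The 8.5% cut is a coarse substitute for the continuous value. With only the stratum in the model, baseline variation inside each stratum stays in the residual, and chance imbalance inside a stratum is left uncorrected. Design does not fully secure that balance either. Randomization used the Visit 7 stratum (SAP 5.3), whereas the analysis uses the baseline stratum (SAP 6.2), with baseline taken as the last of Visits 7-8 (SAP Table 6.2). Patients near 8.5% can change stratum.

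At stake are the precision of one interaction test at 0.10 and of the within-stratum estimates, and whether the two planned responses agree.

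**Working it through.** **The plan's own figures.** SAP 5.2 gives a margin of 0.4, SD 1.1, 320 and 160 completers, and 96% power. The SE is 1.1 × √(1/320 + 1/160) = 0.1065. Then 0.4/0.1065 − 1.96 = 1.80, which gives 96.4% power, so the figure reproduces. Randomized number: 480/0.85 = 564.7, against about 564 stated. The documents give no precision figure for any subgroup.

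**Assumptions.** Baseline is normal, the correlation ρ between baseline and response is 0.3-0.7, and SD 1.1 is the SD of change. One visit stands in for the MMRM, with no missing data.

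**Loss of precision.** Let R² be the share of baseline variance that the 8.5% cut explains: 0.637 at a 50:50 split and 0.490 at 80:20. With the stratum in both models,

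SE without baseline / SE with baseline = √[(1 − ρ²R²)/(1 − ρ²)].

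At ρ = 0.5 and 50:50 this is √[(1 − 0.25 × 0.637)/0.75] = √1.121 = 1.059.

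| ρ | 50:50 | 80:20 |
|---|---|---|
| 0.3 | 1.018 | 1.025 |
| 0.5 | 1.059 | 1.082 |
| 0.7 | 1.162 | 1.221 |

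The loss is partial because the stratum already carries roughly half to two-thirds of the baseline information.

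**Interaction SE at 50:50, ρ = 0.5.** The cells are 160, 80, 160 and 80, so √(2/160 + 2/80) = 0.1936. Without baseline: 1.1 × √0.841 × 0.1936 = 0.195. With baseline: 1.1 × √0.75 × 0.1936 = 0.184. Simulation (480 patients, 2:1 within stratum, baseline SD 0.9, 3,000 runs per setting) gave 0.196 and 0.185.

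**Bias and power in the same simulations.** With no true interaction, the estimate averaged about zero and was rejected at 0.10 in 9-11% of runs, with or without baseline. Power for a true interaction of 0.5 points:

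| ρ | 50:50, without → with | about 67:33, without → with |
|---|---|---|
| 0.3 | 78.4% → 79.4% | 72.9% → 74.0% |
| 0.5 | 82.7% → 86.1% | 75.8% → 80.4% |
| 0.7 | 88.8% → 95.0% | 83.6% → 91.9% |

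**Actual value versus change.** Change equals actual minus baseline. If baseline is a covariate, moving from one response to the other only shifts its coefficient by 1, and every treatment contrast is identical. Without it, the two interaction estimates differ by the chance baseline imbalance between the cells. At 50:50 with baseline SD 0.9, the within-stratum baseline SD is 0.9 × √(1 − 0.637) = 0.542, so that difference has SD 0.542 × 0.1936 = 0.105 points. This is about half the interaction SE of 0.195.

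**Stratum main effect.** At ρ = 0.5 and 50:50, the simulated difference between strata was 0.88 in size (SE 0.160) without baseline. With raw baseline added it was about 0 (SE 0.190). With baseline centred within stratum it was again 0.88 (SE 0.151), and the interaction SE stayed at 0.185. Raw and centred baseline give the same treatment and interaction estimates because, with the stratum in the model, they span the same terms.

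**The case against.** The strongest reply is that the rule has a purpose, only badly named. The stratum is a coarsened copy of the covariate. With raw baseline beside it, the stratum least squares means are evaluated at one common baseline value. If the overall mean is below 8.5%, that value belongs to nobody in the upper stratum, and the stratum main effect collapses. Because actual HbA1c is also analysed, per-stratum means are ordinary output. This stands. A reader might infer that omission brings no benefit and that deleting the sentence is enough. Neither follows, because deletion alone would create the interpretation problem.

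It can also be said that nothing important depends on this. The analysis is one of many unadjusted subgroup looks, outside the graphical scheme of SAP 6.11.2. SAP 6.13.1 allows additional subgroup analyses, so a baseline-adjusted version could be run anyway. SAP 6.2 likewise uses baseline or stratum, not both. All of this stands, and it limits the weight of the point.

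The size is uncertain, since it depends on a baseline distribution that the documents do not give. A reader might bound the lower stratum at 7.0%. That limit applies at Visit 1 (protocol 6.1), before the 8-week lead-in, and no lower limit is set at baseline.

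What the reply does not do is make confounding a valid reason for the interaction. Nor does it show that omission is needed, since centring within stratum keeps the stratum means interpretable without the loss.

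**Conclusion.** The point holds as a minor improvement. For the treatment contrasts within stratum and their interaction, the stated reason is not valid and the omission loses precision: SEs about 2-8% larger at correlations of 0.3-0.5, and about 16-22% larger at 0.7, for splits between 50:50 and 80:20. These figures rest on the assumptions listed with the check. Omission also allows the two planned responses to disagree. The legitimate worry is collinearity with the stratum main effect.

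A reader might go further and infer that the subgroup result is biased or cannot be reconciled with the primary analysis. The check does not support that: the interaction was unbiased with error near its nominal level under both models, and every subgroup model already adds terms to the primary one. The stratum analysis is less directly comparable with the primary analysis, no more than that. The primary non-inferiority test and the multiplicity-adjusted tests do not use this model.

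**What to change.** Replace the exception in SAP 6.13.1 with: *When analyzing HbA1c stratum as a subgroup, continuous baseline HbA1c, centred within stratum, will be retained as a covariate.* Add a note that stratum least squares means are then evaluated at each stratum's own mean baseline. If a reason is to be given, name collinearity with the stratum main effect in place of confounding.

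The cost is one derived variable and that note. Baseline HbA1c is already collected and already used in the other HbA1c subgroup models.
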